A non-contrast cervical spine CT scan at will be obtained for research purposes at UVMMC at the 12 (+/-1) week time point. Final fracture characteristics (angulation, displacement) will be documented based on the 12-week CT scan. Amount of fracture healing will be assessed on CT by a radiologist by the following method¹⁰: 1 mm coronal and sagittal sections across the fracture will be individually analyzed. The radiologist will reconstruct the CT scan to true orthogonal coronal and sagittal images. Each slice will be analyzed for the width of bridging bone as a percentage of the width of the fracture line. The sum total of the widths of bridging bone, divided by the sum total of the fracture widths will be expressed as a percentage of total healing for that patient. This absolute % of bridging bone will be the primary outcome¹⁰. Fracture characteristics (obliquity, angulation, displacement, comminution) on the injury CT scan will be documented for later post-hoc analysis. Additionally, we will also compare our study group results to the union rates documented in the existing literature.

Control subjects:

Our historical control group will be comprised of patients with type II odontoid fractures (defined above) who were previously treated in our spine fracture clinic. Patients will have been injured within the past ten years, and have completed 12 +/-1 weeks of hard collar immobilization. Potentially eligible historical controls will be identified by database query and chart/radiographs review of patients from the fracture clinic. A request will be made of the UVMMC Data Management Office to identify potential control subjects. Identified potential control patients will be approached as outlined under 'Consent Process', below.

If patients are interested in active study participation by coming in for a study visit (research imaging: *Control cohort A: Active control participants*), written informed consent will be obtained in person at UVMMC by designated research personnel. Consented active control subjects will then complete a CT scan of the cervical spine for comparison to those from our study group. If flexion-extension cervical XR were not obtained 11 or more weeks after initiation of hard collar treatment as part of their routine care, flexion-extension cervical XR will be obtained for the study. Additionally, these control subjects will complete VAS Neck and NDI physical function questionnaires.

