Visit Time point	Screening and baseline procedures	4-week visit (within 4 weeks of fracture)	8-week visit (8 +/- 1 weeks after fracture)	12-week visit (12 +/- 1 weeks after fracture)
Informed consent	X*			
Spine Fracture Clinic visit	X (if needed for routine care)	X	X	X
Physical Exam	X	X	X	X
Neck Disability Index		X	X	X
VAS Neck		X	X	X
(Eligibility confirmed by study team after screening labs completed and before study drug administration)				
Endocrinology Clinic visit (only if the patient is not recruited while inpatient)	X*			
Study drug teaching and first dose of Tymlos	X*			
Tymlos self-administration	X* (daily for 8 weeks after drug teaching)			
CMP	X*			
PTH	X*			
Phos	X*			
HbA1c	X*			
AP/Lateral XR	X	X	X	(X if required for routine care)
Flex/Ext XR				X
CT Cervical	X			X*
DEXA	X** (by time of 12-week visit)			
Phone check-in	X* (each week +/- 2 d after first dose for the 8-week treatment period)			

* These procedures are research-driven and deviate from routine care of treatment patients in clinic.

** The DEXA scan is completed for research purposes only if not previously completed within 12 months before consent for routine care purposes.

Spine fracture clinic (and endocrinology visit, for patients not recruited in the inpatient setting) involve medical history under routine care.

Neck Disability Index and VAS Neck physical function are questionnaires given to patients during the clinic visit and prior to medical evaluation. These take less than 10 minutes to fill out, they are validated, and they are standard/routine in many clinic visits. These questionnaires will provide secondary outcome measures.

The study drug (abaloparatide) is an FDA approved medication used to treat osteoporosis. It is a daily subcutaneous injection administered by the patient. This requires patient education.

CMP, PTH, Phos, and HbA1c are laboratory tests performed by venipuncture. Blood work includes complete metabolic profile, phosphorous, parathyroid hormone, and hemoglobin A1c. Many of these patients have osteoporosis at baseline and these tests allow us to screen, quantify, and subsequently manage their osteoporosis. This blood work is standard of care for evaluation and treatment of osteoporosis. In this study, CMP, PTH and Phos will be obtained as screening labs (see Screening Procedures, below). HbA1c

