levels are meant for baseline data collection as they relate to the ability to heal fractures, and are tested with screening labs to prevent need for additional blood draws for research purposes.

AP/Lateral XR and Flex/Ext XR is a standard set of X-rays of the cervical spine used to evaluate the secondary outcome of translational motion at the fracture.

CT Cervical spine is for research purposes at the 12-week mark only. This will be used to measure fracture union rate (the primary outcome).

The DEXA scan is a low dose x-ray scan used as a screening tool recommended for all women over the age of 65. The radiation is so low (significantly lower than a chest x-ray) that this machine and radiation is not formally regulated in the United States. Many of these patients have osteoporosis at baseline and this test allows us to screen, quantify, and subsequently manage their osteoporosis. *In this study*, DEXA scans will be obtained to evaluate bone health as it relates to the ability to heal a fracture. If a patient's T-score is ≤ -2.5 at the spine or hip in a DEXA scan obtained for research purposes, the study team will notify the patient of the finding and refer her/him for follow-up care, as appropriate.

Procedures for control cohort A (active control participants)

Table 2. Research procedures for control patients who provide written consent to active study participation (control cohort A).

Item	UVMMC	Via Mail
Informed consent	X	
Neck Disability Index	X	
VAS Neck	X	
Cervical CT Scan	X	
Flexion-extension cervical x-ray	X**	
Compensation		X*

* After completion of CT scan

** The XR is only obtained for research purposes if a flexion-extension cervical x-ray was not obtained 11 or more weeks after initiation of hard collar treatment as part of their routine care.

Procedures for control cohort B (review-only control participants)

Control cohort B includes subjects who

- (a) Previously had a cervical CT scan obtained after completion of their hard collar treatment under routine care; or
- (b) do not provide written consent to active study participation but provide verbal consent to allow the study team to collect existing information that is available from their treatment in the electronic medical record; or
- (b) are deceased and are not available for informed consent

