Statistical Considerations: Delineate the precise outcomes to be measured and analyzed. Describe how these results will be measured and statistically analyzed. Delineate methods used to estimate the required number of subjects. Describe power calculations if the study involves comparisons. Perform this analysis on each of the primary and secondary objectives, if possible.

Primary outcome will be % bridging bone on CT scan at 12 weeks as described previously based on 1 mm sagittal and coronal cuts. The study radiologist evaluating the primary outcome will be blinded to patient group (treatment vs. historical control). Secondary outcomes will include VAS Neck and NDI scores, and motion on flexion/extension radiographs.

Assuming 60% nonunion rate in our historical control group and 20% in our study group, with alpha = 0.05 and 80% power, we would need to enroll 44 patients in a randomized trial (22 control, 22 study patients) to show a statistical difference. This study is intended as an initial pilot study to suggest efficacy, and further inform a future randomized controlled trial. We see 15-20 new type II dens fractures treated non-operatively per year in our fracture clinic, and estimate the initial pilot of 10 treatment patients + 12 control subjects can be completed within 2 years.

Data analysis will be based on multi-variate regression using ANOVA, with $p < 0.05$ recognized as a significant difference. Plan is for as treated analysis; if there are patients who receive only partial course of study drug for any reason, they will be evaluated descriptively as a separate group. Additionally, we will also compare our study group results to the union rates documented in the existing literature.

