Historical Comparison Subjects

Inclusion Criteria (all must be yes)

1. Age 50 years or older at time of fracture
2. Anderson and D'Alonzo type II dens fracture identified on cervical spine CT, with or without a C1 ring injury. Type II dens fractures are defined as involving the area of the dens between the inferior aspect of the anterior C1 ring and not extending into the superior articular facets of C2.
3. Fracture injury occurred within 10 years before consent
4. The patient completed 12 (+/- 1) weeks of hard collar immobilization

Exclusion Criteria (all must be no)

5. Any history of prior teriparatide or abaloperatide use
6. Use of denosumab in the past year

Inclusion of Minorities and Women: Describe efforts to include minorities and women. If either minorities or women are excluded, include a justification for the exclusion.

Women will be included in the study whenever the eligibility criteria are met. Every effort will be made to recruit minorities. Recruitment efforts will not differ by sex or by ethnicity.

Inclusion of Children: Describe efforts to include children. Inclusion is required unless a clear and compelling rationale shows that inclusion is inappropriate with respect to the health of the subjects or that inclusion is inappropriate for the purpose of the study. If children are included, the description of the plan should include a rationale for selecting or excluding a specific age range of children. When included, the plan must also describe the expertise of the investigative team in working with children, the appropriateness of the available facilities to accommodate children, and the inclusion of a sufficient number of children to contribute to a meaningful analysis relative to the purpose of the study. Provide target accrual for this population. Identify whether children are wards of the state. **If children are excluded** then provide appropriate justification.

The fracture of interest occurs very rarely in minor subjects, and the safety and effectiveness of the study drug has not been established in pediatric patients. Children will not be included in this study.

For protocols including the use of an investigational drug, indicate whether women of childbearing potential have been included and, if not, include appropriate justification.

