i. Once a prospective subject is identified, who initiates the informed consent discussion and answers questions presented by the subject or the subject's family?

Designated key personnel of the study will be able to initiate the informed consent discussion and answer questions presented by the subject or the subject's family.

ii. Where (in what setting) is the informed consent process initiated? How much time is the subject given to decide?

For the treatment subjects, ideally the informed consent process will be initiated in the hospital setting within a

day or two after the diagnosis. If the patient is diagnosed at an outside facility and presents to the outpatient spine clinic for follow up, the informed consent process would be initiated there.

For potential control subjects who are living at time of identification and have not previously had a cervical CT under routine care after completion of hard collar treatment; the informed consent process will be initiated either in person or via letter or email from [name]. Designated research personnel will follow-up in person or by phone within two weeks to inquire about interest in study participation. The same, approved recruitment phone script will be used whether it is in person or by phone.

- For participants interested in active study participation (*control cohort A*), written informed consent will be obtained in person at UVMMC in a private room, prior to study imaging or administration of the study questionnaires.
- For eligible control subjects who indicate at time of recruitment phone call that they are not interested in active study participation, the patient will be invited to verbally consent to participation in *control cohort B*. A verbal consent script has been developed for this purpose.

Potential control subjects who are living at time of identification and have previously had a cervical CT under routine care after completion of hard collar treatment will be approached using the approved verbal consent script described above. The verbal consent script offers the opportunity for (passive) participation in *control cohort B* and introduces the researcher as a member of [name] research team.

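### Control CTs and the cohort A VAS/NDI are not tied to 12 weeks, so the 12-week primary comparison is confounded with time since injury and the analysis plan does not address it

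*Combined protocol and SAP*

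**What the plan says.** **Treated patients.** Statistical Considerations states "Primary outcome will be % bridging bone on CT scan at 12 weeks". Table 1 places the research CT in the column headed "12-week visit (12 +/- 1 weeks after fracture") and marks it with the footnote "These procedures are research-driven and deviate from routine care of treatment patients in clinic". VAS Neck and NDI are collected at 4, 8 and 12 weeks.

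**Control cohort A.** Study Design (Control subjects) says "Consented active control subjects will then complete a CT scan of the cervical spine for comparison to those from our study group". Under Consent Process, written consent comes first, then imaging and questionnaires. The only limit on elapsed time is in the eligibility criteria: "Fracture injury occurred within 10 years before consent", together with completion of 12 +/-1 weeks in the collar. Consent Process offers cohort A to living controls who "have not previously had a cervical CT under routine care after completion of hard collar treatment". The questionnaire section has controls complete VAS and NDI once, in person.

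**Control cohort B.** Living controls who "have previously had a cervical CT under routine care after completion of hard collar treatment will be approached using the approved verbal consent script" go to cohort B. Group (a) of that cohort is defined by "Previously had a cervical CT scan obtained after completion of their hard collar treatment under routine care", with no upper time limit. The cohort also takes in people who decline a visit and people who have died; their existing records are used. Sources of Materials lists radiographs, but not CT, for cohort B.

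**Analysis.** Statistical Considerations gives multivariate regression using ANOVA with a 0.05 threshold. It names no covariate, and no matching, restriction or sensitivity analysis for time since injury. It does not say which treated VAS/NDI visit is compared with the controls.

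**The concern.** The outcome is defined at 12 weeks, but only the treated group is scheduled to supply it then. Cohort A is made up of controls with no earlier routine post-collar CT, so it has no scan near 12 weeks to fall back on unless the research visit happens to come soon after the collar. Group and time since injury are therefore confounded in the CT comparison, and in the VAS/NDI comparison wherever cohort A's research values are used.

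Two separate problems follow. The first is timing: fractures imaged months or years later have had longer to bridge, which would tend to raise control values and mask a drug effect. The second is selection: controls must have survived, be able and willing to attend, or have had some clinical reason for a routine scan. That could push control values up or down.

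The pilot is meant to suggest efficacy and inform a randomised trial. A control estimate taken at unspecified times, but reported as a 12-week result, could mislead the planning of that trial.

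**Working it through.** **1. Timing by group and outcome.**

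| | Treated | Cohort A | Cohort B |
|---|---|---|---|
| CT | 11 to 13 weeks | after consent; injury up to 10 years earlier | group (a): routine scan after collar completion, no upper limit; others: only if one exists |
| VAS/NDI | 4, 8, 12 weeks | once, at the research visit | past routine values, if recorded |
| Flexion/extension film | 11 to 13 weeks | routine film from 11 weeks after the start of collar treatment if one exists, otherwise at the research visit | routine films, if any |

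Ten years is 10 × 365.25 / 7 = 522 weeks, about 43 times 12 weeks. That is the maximum, not the expected interval. Motion is the smallest gap, because a routine film is used where there is one.

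**2. Could the regression absorb it?** No time covariate is named. If one were added, all treated scans would still lie at 11 to 13 weeks. Bringing a scan taken years later back to 12 weeks would then be extrapolation: the treated data carry no information on later times, and there are only 22 patients.

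**3. The plan's own sample size.** It assumes nonunion of 60% versus 20%, alpha 0.05 and 80% power. With the arcsine formula, h = 2·asin(√0.6) − 2·asin(√0.2) = 0.845, and n = 2·((1.960 + 0.842)/h)² = 21.99. That is 22 per group, 44 in total, as stated. This figure is for a randomised trial on a binary outcome. For the pilot's 12 controls and 10 treated at the same rates (two-sided, pooled normal approximation):
- pooled rate (12 × 0.6 + 10 × 0.2)/22 = 0.418
- null SE √(0.418 × 0.582 × (1/12 + 1/10)) = 0.211
- alternative SE √(0.24/12 + 0.16/10) = 0.190
- power Φ((0.4 − 1.960 × 0.211)/0.190) = about 47%

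**4. Illustration of masking on the continuous outcome.** Two-sided t-test at 0.05, 12 controls and 10 treated, 20 df, critical t 2.086, √(1/12 + 1/10) = 0.428. From the noncentral t, 80% power needs an effect of 1.261 SD. If all control scans are shifted up by s, the effect seen is 1.261 − s:

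| Assumed s (SD) | Effect seen (SD) | Power |
|---|---|---|
| 0 | 1.261 | 0.800 |
| 0.25 | 1.011 | 0.613 |
| 0.50 | 0.761 | 0.395 |
| 0.75 | 0.511 | 0.206 |

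The effect and every shift are assumptions. With no shift there is no distortion.

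**5. Precision if only k controls have a CT near 12 weeks.** The 95% CI half-width in SD is t(0.975, k + 8) × √(1/k + 1/10):
- k = 3: 2.201 × 0.658 = 1.45
- k = 6: 2.145 × 0.516 = 1.11
- k = 12: 2.086 × 0.428 = 0.89

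The values 3 and 6 are assumed, as the documents do not say how many such controls exist.

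**The case against.** The study openly declares a historical control group and pilot status, and no such design removes selection. That stands, and it limits the weight of the point. It does not answer the timing problem: a different assessment time is not inherent in using historical controls, and the plan neither labels nor handles it. Blinding the radiologist to group does not change when the scan was taken.

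Four stronger readings are tempting, and the documents do not support them.

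- **That late scanning could manufacture a drug effect.** The evident timing mechanism is later healing, which favours controls. A false positive would have to come from selection, a separate matter whose direction is unknown.
- **That the pilot loses power from a planned 80%.** The plan claims 80% only for 22 per group. It states no effect in SD units, and it does not say that all 12 controls will have a CT. People who decline a visit or have died may have none, so 12 is an upper bound.
- **That cohort B CTs are left out of the primary outcome.** Their absence from the cohort B materials list suggests this. But Procedures for control cohort B says the records support analysis of available outcomes, and the opening of Sources of Materials counts CT as primary-outcome material and draws on existing records. The sections need reconciling.
- **That cohort B scans fall near 12 weeks and so rescue the comparison.** Usual follow-up runs to 12 weeks, but Table 1 marks the 12-week CT as research-driven, and nothing says when routine post-collar scans were taken.

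It is also fair to say that routine VAS/NDI may exist for cohort A, because the questionnaires are described as standard practice for all spine patients at clinic. The documents do not say how far back that goes, and the cohort A sources list names only the study questionnaires.

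**Conclusion.** The point holds and should be fixed. Followed as written, the plan compares treated CTs at 11 to 13 weeks with control CTs taken at unspecified times, up to about 10 years after injury in cohort A, and calls the result a 12-week outcome. The same mismatch affects the cohort A research VAS/NDI.

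Confidence is high for the mismatch and for its absence from the analysis plan. It is not high for the size of the bias: the documents give no late-healing rate and no measure of selection. Timing would mainly mask an effect; selection could act either way. For these two separate reasons, neither a null nor a positive result could be attributed to the drug alone. The fall in power to about 61%, 40% or 21% shows only how sensitive a comparison of this size would be, under an assumed 1.26 SD effect and assumed shifts in every control scan.

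**What to change.** 1. Describe the main CT contrast as treated at 12 weeks versus controls at the time scanned. State in advance that neither a null nor a positive result can be attributed to the drug alone, giving timing (mainly masking) and selection (either direction) as separate reasons.
2. Record days from injury to CT, questionnaires and flexion/extension film for every control, and report them by cohort. Reconcile the cohort B list in Sources of Materials with the text on existing CTs.
3. Prespecify a sensitivity analysis limited to control CTs in a fixed window near 12 weeks, which the investigators set before any control CT is read. Acknowledge that it may hold few or no controls.
4. Compare treated 12-week VAS and NDI with routine 12-week chart values for controls where these exist, and report late cohort A values separately. Amend the cohort A sources list, and the consent wording if needed, to cover this. For motion, use the routine film nearest 12 weeks where one exists.

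The cost is protocol wording, chart abstraction and a small document amendment; no new imaging is needed. The statistical price is fewer controls in the time-matched comparisons: a CI half-width of about 1.45 or 1.11 SD with an assumed 3 or 6 controls, against 0.89 SD with 12. These steps limit and disclose the confounding; they do not remove it.

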Eligible patients will receive standard treatment of 12(+/-1) weeks of rigid hard collar immobilization, as well as an 8-week course of PTH analog during this time. Drug will be initiated as soon after the injury as possible, and at the latest 4 weeks from injury which will allow for completion of 8 weeks of drug administration during the period of hard collar immobilization. Teaching on drug administration will be provided for enrolled patients and their caregiver, if applicable, by designated study personnel prior to drug initiation – either while inpatient, or at the outpatient endocrinology clinic visit. Treatment subjects will otherwise receive the routine care that was provided to historical controls in terms of length of hard collar immobilization spine fracture clinic follow-up and radiographic evaluation. Treatment subjects will be followed with weekly phone calls (see Table 1) by clinical personnel on the study team for the duration of the 8-week treatment.

Study participants will be followed at the spine fracture clinic according to our usual protocol every 4 weeks +/- 1 week (from the date of injury) out to 12 weeks. All patients will fill out VAS Neck and Neck Disability Index (NDI) physical function questionnaires at each clinic visit. Use of narcotic pain medication will be collected at each clinic visit under routine care.

DEXA scans will be obtained for all participants to assess baseline bone density. If a patient has had a DEXA scan for routine care within the 12 months prior to consent, that scan will be used as the baseline test and a separate test for research will not be ordered. If needed, baseline DEXA will need to be completed after consent and by time of the 12 week visit.

All radiographs for treatment subjects will be obtained as part of routine care. These include AP/Lateral at each of the 4 (+/-1) week and 8 (+/-1) week clinic visits, and Flex/Ext at the 12 (+/-1) week clinic visits. Final (12 +/-1 week) flexion/extension radiographs will be evaluated for translational motion at the fracture site measured at the posterior cortex of the dens and evaluated by the following criteria: None, Minimal (<2 mm), Moderate (2-4 mm), Mobile (>4 mm).

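### Control flexion/extension films have no upper time limit and no selection rule, so the secondary motion comparison can mix drug effect with time since injury

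*Combined protocol and SAP*

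**What the plan says.** **Treated subjects.** Study Design (Treatment subjects) states: "Final (12 +/-1 week) flexion/extension radiographs will be evaluated for translational motion at the fracture site". Motion is placed in one of four grades, from none to more than 4 mm. Table 1 counts the 12-week visit from the fracture. The films are not a research extra: "All radiographs for treatment subjects will be obtained as part of routine care".

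**Cohort A (active controls).** Study Design (Control subjects) makes a new film conditional: "If flexion-extension cervical XR were not obtained 11 or more weeks after initiation of hard collar treatment as part of their routine care", then "flexion-extension cervical XR will be obtained for the study". The footnote to Table 2 repeats the condition. Both count from the start of the collar, and neither gives a latest date. The eligibility limit for historical comparison subjects is "Fracture injury occurred within 10 years before consent".

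**Cohort B (review-only controls, including the deceased).** The protocol collects applicable radiographs from routine care and gives no time window for them.

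**Link between the groups.** Study Design (Treatment subjects) says "Treatment subjects will otherwise receive the routine care that was provided to historical controls", and the sentence goes on to name clinic follow-up and radiographic evaluation.

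**Analysis.** Statistical Considerations lists flexion/extension motion as a secondary outcome. It names a multivariate regression using ANOVA without listing covariates, and plans 10 treated and 12 control subjects.

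**The concern.** The motion grade is meant to show how stable the fracture is at the end of the collar period. For a treated subject it describes week 11 to 13. For a control it may describe the same weeks, some months later, or a research visit years later, and all of these count alike. A fracture that unites late would move less on a late film. One that stays ununited may move as much or more; the protocol's own background mentions instability as a less common result of non-union. Either way, the contrast between groups would carry elapsed time as well as the drug. The pilot is meant to inform a randomized trial, so a motion difference of unclear origin could be carried forward.

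**Working it through.** The protocol gives no expected value, sample size or distribution for motion, so there is no stated figure to reproduce. Its total of 44 for a randomized trial concerns nonunion and does not bear on this point. The check compares time windows.

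**1. Width of the windows.**
- Treated: 11 to 13 weeks after fracture = 11 × 7 to 13 × 7 = days 77 to 91. Width 2 weeks.
- Control, earliest: 11 weeks after collar start (day 77 of the collar).
- Control, latest: none stated. The only outer bound is 10 years from fracture to consent: 10 × 365.25 / 7 = 521.8 weeks. A research film follows consent, so it could fall slightly later still.
- Control width: 521.8 − 11 = about 511 weeks.

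This is the range that the rules permit. The documents give no distribution of film dates.

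**2. The two anchors.** Treated films count from fracture, control films from collar start. Suppose the collar starts d days after injury (d is not documented; I take 0 to 14 as an illustration). A film at collar week w then falls on day 7w + d after injury.
- w = 11: day 77 + d, inside days 77 to 91 for d up to 14.
- w = 12: day 84 + d, inside for d up to 7.
- w = 13: day 91 + d, inside only for d = 0.

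The mismatch also works the other way. With d = 7, a routine film on day 80 after injury lies inside the treated window, but it is at 73 / 7 = 10.4 weeks of collar. It fails the 11-week condition, so a new research film would be called for.

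**3. Weight of one late film.** If all 12 planned controls contribute a film, each is 1/12 = 8.3% of the control distribution on a four-grade scale. Three late films would be 3/12 = 25%.

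**4. Whether adjustment would help.** No covariate is named. Adding time since injury would not repair the comparison, because every treated film lies within the same 2 weeks. The adjustment would rest on a time trend estimated from at most 12 controls and carried back to week 12.

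**5. Whether time-matched control films exist.** Treated subjects' films are called routine care, and treated subjects are said to get the routine radiographic evaluation given to controls. Together these imply that many controls had a film near 12 weeks. The fallback film in cohort A implies that some did not. No count is given.

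**The case against.** The strongest reply is that the quoted sentence governs when to order a new x-ray and is not an analysis window. It puts the routine film first: a control with a film at week 12 of the collar gets no new one, and that film is available. If routine films are common, the fallback is rare and any distortion is small. If they are scarce, a strict window removes many of only 12 controls. This stands as a limit on the likely size. It does not supply an upper limit or a selection rule, and no other section does.

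A reader might infer more than the documents support:
- **That the plan discards the routine 12-week films, or that a time-matched comparison is lost.** It is not. Routine films come first in cohort A, and radiographs of cohort B, including deceased controls, are already collected. The fault is that later films count equally.
- **That motion is the only outcome that could be matched in time.** Neck pain (VAS) and disability (NDI) scores are described as routine at clinic visits, and Sources of Materials lists past routine scores for cohort B where recorded.
- **That in-window films surely exist, or that only a few controls would drop out.** The first is an inference from one general sentence about treated subjects. The second has no figure behind it.
- **That the ratio of window widths measures bias, or that its direction is known.** Neither follows. Ten years is an eligibility limit, and no film dates are given.

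It is also fair that motion is one of several secondary outcomes in a pilot. The primary CT outcome is not touched by this point.

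**Conclusion.** The point holds. As written, a motion grade at 11 to 13 weeks after fracture can be compared with one taken at any time from week 11 of the collar to about 10 years after fracture. There is no rule for choosing among films and no account of time since injury. This goes beyond missing detail, because the stated cohort A rule itself produces films that are not time-matched. Direction and size cannot be fixed from the documents; the one usable scale is 8.3% of the control group per late film, if all 12 controls contribute.

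Confidence is high that the window is open-ended and the selection rule absent. It is moderate that enough in-window control films exist, since that rests on the routine-care statement. The change is worth making before analysis.

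**What to change.** Add to Statistical Considerations, for the motion outcome:

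1. The group comparison uses, for each control, the film nearest to 12 weeks after injury and within 11 to 13 weeks, the same anchor as for treated subjects. Films may come from cohort A and from cohort B, including deceased controls.
2. Record injury date, collar start date and film date for every control. In a sensitivity analysis, count the 11 to 13 weeks from collar start, and check that the choice of anchor does not drive who is excluded.
3. Report later routine films and research-visit films separately, each with time since injury, outside the group comparison.
4. State how many controls lack an in-window film.

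**Cost.** Analysis wording and films already in the record; no added visit, imaging or change in care. The price is that an unknown number of the 12 planned controls may leave this comparison, so its precision could fall. Selection is reduced but not removed: every control must have completed 12 +/- 1 weeks of collar, and living members of cohort B must consent.
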